5.1.1.4.6 Other Analyses

5.1.1.4.6.1 Nonscalp Hair Growth

Starting at Week 8, subjects will be queried at each visit whether they have noticed any hair growth in nonscalp areas (yes/no) and this response will be captured in the eCRF. If judged by the investigator as clinically significant, nonscalp hair growth may be reported as an AE.

The nonscalp hair growth will be summarized separately with a frequency distribution by treatment group.

5.1.1.5 Subgroup Analyses

Subgroup analyses are not planned but might be performed as Ad hoc analyses after database lock.

5.1.1.6 Interim Analyses

Not applicable.

5.2 Changes in the Conduct of the Study or Planned Analyses

5.2.1 Changes in the Conduct of the Study

Not applicable.

5.2.2 Changes to Analyses Prior to Database Lock

Not applicable.

- 6. Data Handling and Analysis Conventions
- 6.1 Study Treatment Conventions

[figure not shown]
6.1.1 Analysis Days

- Study days will be calculated as visit date baseline date (day 1) + 1 if visit date is on or after baseline date; otherwise it will be calculated as visit date -baseline date (day 1).
- Treatment period is defined as days between the date of study treatment start and the date of the study treatment end.

6.1.2 Missing/Incomplete Treatment End Date

If the investigator is unable to provide the treatment end date, treatment end date will be imputed to the last treatment application, or early exit, or week 24 visit, whichever is the first.

6.3 Missing Date Information for Adverse Events

Partial AE dates will be imputed using the below methods.

Partial AE onset date will be imputed as follows:

- 1) If day is missing but month is not, impute the date as the first day of the month;
- 2) If both day and month are missing, impute the date as 01 Jan;
- 3) If imputed onset date is before the first treatment, yet the corresponding AE was not observed pre-treatment, then impute the onset date as the first treatment date.

Imputed partial AE onset date will only be used to determine the AE onset cycle.

Partial AE stop date will be imputed as follows:

- 1) If day is missing but month is not, impute the date as the last day of the month;
- 2) If both day and month are missing, impute the date as 31 Dec.

The date of first increase in severity to moderate, if a partial date, will be imputed as follows:

The date of first increase in severity (to moderate or severe), if a partial date, will be imputed as follows:

1) If day is missing but month is not, impute the date as the 15th of the month;

- 2) If both day and month are missing, impute the date as 15 June;
- 3) If imputed partial date is before the first treatment, and the corresponding AE was observed during treatment study period, then impute the date as the first treatment date;
- 4) If imputed partial date is before the onset date or the date of first increase in severity, then impute the partial date as the later of these two dates.

Imputed partial AE dates will only be used to determine treatment-emergent AE (TEAE). All partial dates will be listed "as is" in the data listings.

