5.1.1.4.2 Adverse Events

[figure not shown]
An AE is defined as any untoward medical occurrence in a subject administered a pharmaceutical product and that does not necessarily have a causal relationship with this treatment. Adverse events are collected both for the screening/baseline period pretreatment (which are referred to as pretreatment AEs) and for the follow-up period after treatment is initiated (which are referred to as postbaseline AEs). Adverse events will be summarized using the concept of treatment-emergent adverse events (TEAEs). TEAE is a postbaseline AE where:

- a) there is no pretreatment AE of the same MedDRA primary system organ class (SOC) and preferred term (PT); or
- b) the maximum severity during the postbaseline period is greater than the maximal severity of any pretreatment AE of the same MedDRA primary SOC and preferred term during the screening/baseline period; or
- c) the AE reports as a serious AE (SAE) during the postbaseline period

Analysis of the incidence of TEAEs will be performed over the entire study period, and the incidence of TEAEs will be presented and summarized as follows:

- (1) Overall AE, treatment related TEAE, serious AE, deaths, AEs leading to discontinuation and Non-scalp hair growth.
- (2) TEAEs by primary SOC in alphabetical order, PT and severity (maximum severity). The maximum severity of a TEAE experienced by a subject is determined by the greatest severity recorded on the eCRFs for the subject's given TEAE.
- (3) Common (>=2%) TEAEs by Preferred Term
- (4) Treatment related TEAEs by primary SOC in alphabetical order, and preferred term.
- (5) Treatment-emergent serious AEs (SAE) by SOC in alphabetical order, and preferred term.
- (6) TEAEs leading to treatment discontinuation by SOC in alphabetical order, and preferred term
- (7) Treatment-emergent SAE with fatal outcome by primary SOC in alphabetical order, and preferred term. Subject listings will be generated for all AEs, SAE, Deaths, and AEs leading to study discontinuation.

Participant listings will be provided for all AEs, SAEs, AEs leading to study treatment discontinuation, and death (if occurred).

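### The SAP's rule for partial worsening dates can move a worsening recorded as pre-dose onto the first-dose date and so create a false TEAE (minor)

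*SAP*

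**What the plan says.** SAP Section 6.3 gives four rules for a partial date of first increase in severity.

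- Rule 1: "If day is missing but month is not, impute the date as the 15th of the month".
- Rule 2: "If both day and month are missing, impute the date as 15 June".
- Rule 3, which substitutes the first-dose date, reads: "If imputed partial date is before the first treatment, and the corresponding AE was observed during treatment study period, then impute the date".
- Rule 4, which takes whichever of two dates is later, reads: "If imputed partial date is before the onset date or the date of first increase in severity, then impute the partial date as".

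The rules for a partial onset date, in the same section, also contain a reset to first treatment, but a narrower one. It applies when the imputed onset precedes first treatment, "yet the corresponding AE was not observed pre-treatment, then impute the onset date as the first treatment date".

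Two sentences in Section 6.3 state what the imputed dates are for. After the onset rules: "Imputed partial AE onset date will only be used to determine the AE onset cycle". At the end of the section: "Imputed partial AE dates will only be used to determine treatment-emergent AE (TEAE").

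SAP Section 5.1.1.4.2 defines a TEAE by any of three criteria. Criterion (a) needs no pretreatment AE of the same system organ class and preferred term. Criterion (b) is met when "the maximum severity during the postbaseline period is greater than the maximal severity of any pretreatment AE" of the same class and term. Criterion (c) covers serious AEs in the postbaseline period.

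**The concern.** Resetting an uncertain date to first dose is a usual conservative choice when the order of worsening and dosing is unknown. Rule 3 goes further. Its two conditions are that the imputed date precedes first treatment and that the AE was seen on treatment. Both can hold when the recorded month or year already shows that the worsening came before dosing. The rule then replaces something known with something contrary to the record.

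The date matters because criterion (b) compares maximum severity before and after the start of treatment. Moving a pre-dose worsening to the first-dose date lowers the pretreatment maximum and leaves the postbaseline maximum unchanged. An AE that merely continued at the same severity is then counted as having worsened on treatment. What is at stake is the accuracy of the TEAE tables.

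**Working it through.** The documents give no figure to reproduce, so the check is to apply the rules to example records. The dates below are assumed for illustration. In each record the AE is mild at a pre-dose onset, becomes moderate at the worsening, and is still present on treatment. The AE is non-serious, so criterion (c) does not apply, and it has a pretreatment record, so criterion (a) does not apply. Only (b) can make it a TEAE. The first-dose date is counted as postbaseline.

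**Rules as written**

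| Recorded worsening | Onset | First dose | Rule 1 or 2 | After rules 3 and 4 | Pre / post maximum | TEAE under (b) |
|---|---|---|---|---|---|---|
| Feb 2017 | 5 Jan 2017 | 20 Mar 2017 | 15 Feb 2017 | 20 Mar 2017 | mild / moderate | yes |
| 2016 | 5 Dec 2016 | 10 Jan 2017 | 15 Jun 2016 | 10 Jan 2017 | mild / moderate | yes |
| Mar 2017 | 5 Jan 2017 | 20 Mar 2017 | 15 Mar 2017 | 20 Mar 2017 | mild / moderate | yes |
| 2017 | 1 Jun 2017 | 20 Jul 2017 | 15 Jun 2017 | 20 Jul 2017 | mild / moderate | yes |

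In the first two rows the recorded part of the date places the worsening before first dose. The true comparison is moderate before and moderate after, so (b) should fail. Rule 4 cannot repair this, because it only moves dates later. In the last two rows the order is unknown and the reset is defensible.

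The first row does not depend on the early onset date; any onset up to the end of February gives the same result. The latest possible worsening, 28 February, is 20 days before dosing on 20 March. In general, a screening period that crosses a month-end is enough.

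**With a compatibility condition on rule 3** (same month and year as first dose, or same year with month unknown)

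- Feb 2017: stays at 15 Feb 2017; moderate / moderate; not a TEAE under (b).
- 2016: 15 Jun 2016, then 5 Dec 2016 by rule 4 (onset); moderate / moderate; not a TEAE under (b).
- Mar 2017 and 2017: still moved to first dose; still TEAEs.

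**Comparison with SAP Section 6.4.1.** For medication start dates, the recorded year and month are compared with first dose before anything is imputed. A matching month and year, or a matching year with month unknown, takes the first-dose date. An earlier year or month stays earlier. This is the check that rule 3 lacks.

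**Size per record.** Planned group sizes are 80 and 72 (SAP Section 4.1), taken here as the safety denominators.

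- One case: 1/80 = 1.25 percentage points on setipiprant; 1/72 = 1.39 points on placebo.
- Two cases of one preferred term in one arm: 2/80 = 2.5%; 2/72 = 2.8%. Either would pass the 2% threshold of the common-TEAE table.

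A case adds its full amount only if the subject has no other TEAE of that term.

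**The case against.** The strongest objection is that the rule may have nothing to act on. Protocol Sections 6.3.1 and 12.2 list the AE information to be recorded, and a date of first severity increase is not on the list. Neighbouring SAP text looks generic: an onset cycle in a trial of continuous daily dosing, a last treatment application for an oral tablet, rescue medication. If the date is not collected, the effect is zero. The case report form is not among the documents, so this cannot be settled. The objection stands as a limit on size. It does not make the rule correct.

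The affected set is also narrow. The AE must begin between consent and dosing, worsen before dosing, have a partial worsening date whose known part lies wholly before dosing, and persist on treatment. Partial dates are shown unaltered in the listings, so such records can be found. This stands too.

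A reader might infer three stronger things that the documents do not support.

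- That the safety comparison is biased. The same rule applies to both randomised arms and acts on pre-dose events, so no systematic difference is expected, and the AE analyses are descriptive.
- That the onset reset has the same fault. It already requires that the AE was not observed before treatment, and no failing case has been shown.
- That the onset-cycle sentence leaves AEs with partial onset dates without any TEAE status. That means ignoring the section's closing sentence, which assigns imputed AE dates generally to TEAE determination. The two sentences conflict, but the matter is editorial.

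Finally, rule 3 would be harmless if its second condition meant that the worsening itself was seen on treatment. The text refers to the AE, not to its worsening.

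**Conclusion.** Rule 3 is wrong as written, at minor severity. It can override a recorded pre-dose month or year and so turn an AE that worsened before dosing into a TEAE under criterion (b).

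The conclusion rests on three readings: that observed on treatment means the AE was present then, that the first-dose date counts as postbaseline, and that worsening dates are collected. Without the third, the rule is inert. The documents give no count of partial worsening dates. The number affected is probably very small and may be zero, and no shift in favour of either arm is expected. Complete pre-dose dates are not moved, and the reset remains reasonable where the order is truly unknown.

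**What to change.** Add one condition to severity-date rule 3: reset to first treatment only if the recorded part of the date (month and year, or year alone) is compatible with a date on or after first treatment. Otherwise keep the imputed pretreatment date, subject to rule 4. This follows the logic of SAP Section 6.4.1. No change to the onset reset is needed.

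As an editorial clean-up, delete the sentence that limits imputed onset dates to an onset cycle, so that TEAE determination is the single stated use.

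The cost is one amended sentence, one deleted sentence and one extra condition in the date derivation. The TEAE count may fall slightly. If the case report form does not collect worsening dates, the severity-date rules have no use in this trial, and the SAP could say so.

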6.4 Missing/Incomplete Date for Prior and Concomitant Medications

For prior or concomitant medications, including rescue medications, incomplete (ie, partly missing) start dates and/or stop dates will be imputed. When the start date and the stop date are both incomplete for a patient, the start date will be imputed first. If the stop date is complete (or imputed) and the imputed start date is after the stop date, the start date will be imputed using the stop date. Imputed partial medication start/stop dates will only be used to determine prior or concomitant medication. All partial dates will be listed "as is" in the data listings.

6.4.1 Missing/Incomplete Start Date

The following rules will be applied to impute the missing numeric fields for an incomplete prior or concomitant medication start date.

• Missing month and day

- 1) If the year of the incomplete start date is the same as the year of the first dose of study treatment, the month and day of the first dose of study treatment will be assigned to the missing fields;
- 2) If the year of the incomplete start date is before the year of the first dose of study treatment, December 31 will be assigned to the missing fields;
- 3) If the year of the incomplete start date is after the year of the first dose of study treatment, January 1 will be assigned to the missing fields.

• Missing month only

If only the month is missing, the day will be treated as missing and both the month and the day will be replaced according to the above procedure.

• Missing day only

1) If the month and year of the incomplete start date are the same as the month and year of the first dose of study treatment, the day of the first dose of study treatment will be assigned to the missing day;

- 2) If either the year of the incomplete start date is before the year of the date of the first dose of study treatment or if both years are the same but the month of the incomplete start date is before the month of the date of the first dose of study treatment, the last day of the month will be assigned to the missing day;
- 3) If either the year of the incomplete start date is after the year of the date of the first dose of study treatment or if both years are the same but the month of the incomplete start date is after the month of the date of the first dose of study treatment, the first day of the month will be assigned to the missing day.

6.4.2 Missing/Incomplete End Date

The following rules will be applied to impute the missing numeric fields for an incomplete prior or concomitant medication stop date. If the date of the last dose of study treatment is missing, impute it as the method in the Section 6.1.2. If the imputed stop date is before the start date (imputed or nonimputed start date), the imputed stop date will be equal to the start date.

• Missing month and day

- 1) If the year of the incomplete stop date is the same as the year of the last dose of study treatment, the month and day of the last dose of study treatment will be assigned to the missing fields;
- 2) If the year of the incomplete stop date is before the year of the last dose of study treatment, December 31 will be assigned to the missing fields;
- 3) If the year of the incomplete stop date is after the year of the last dose of study treatment, January 1 will be assigned to the missing fields.

• Missing month only

If only the month is missing, the day will be treated as missing and both the month and the day will be replaced according to the above procedure.

• Missing day only

- 1) If the month and year of the incomplete stop date are the same as the month and year of the last dose of study treatment, the day of the last dose of study treatment will be assigned to the missing day;
- 2) If either the year of the incomplete stop date is before the year of the date of the last dose of study treatment or if both years are the same but the month of the incomplete stop date is before the month of the date of the last dose of study treatment, the last day of the month will be assigned to the missing day;

3) If either the year of the incomplete stop date is after the year of the date of the last dose of study treatment or if both years are the same but the month of the incomplete stop date is after the month of the date of the last dose of study treatment, the first day of the month will be assigned to the missing day.

6.5 Imputation of Primary Efficacy Measurements (TAHC and SSA)

Missing data of all TAHC endpoints and SSA (blinded and unblinded) will be imputed up to Week 24 using last observation carried forward (LOCF) as follows: when there is no observation in a particular visit window, the latest non-missing observation prior to that visit window will be carried forward and used for analysis for that particular window, whether from a scheduled or unscheduled visit. Imputation will be applied to postbaseline visits up to Week 24 only. If missing data occur at scheduled visit(s) immediately following baseline, the baseline value will be carried forward for imputation. Analyses of Week 32 data will be based on observed cases without data imputation.

- Section 6.5: Clarification was made to indicate that the LOCF missing data imputation will be done for all TAHC endpoints and SSA (blinded and unblinded). In addition, more details of how the LOCF algorithm will be done are provided.

ALLERGAN

Analysis Plan for 1922-201-002 Amendment 2

Date (DD/MMM/YYYY)/Time (PT)	Signed by:	Justification
